6.2. Participant Discontinuation/Withdrawal from the Study

In all cases of subject withdrawal or discontinuation, the reason for withdrawal must be recorded in the eCRF/CRF and in the subject's medical records. If the reason is not known, the subject must be followed to establish whether the reason was due to an AE, and, if so, this must be reported in accordance with the procedures in Section [7.5.8](#).

Evaluations should be performed on all subjects who participate but do not complete the study according to protocol. Dropouts may be replaced at the request of the sponsor. The investigator will make every effort to contact subjects lost to follow-up. Subjects who have an ongoing AE at the time of study completion will be followed until the event resolves, or until the sponsor and the Investigator agree that further follow-up is not medically necessary.

6.3. Lost to Follow-up

Subjects are considered lost to follow-up if the subject does not return to the clinic and attempts to contact the subject are unsuccessful. Efforts must be made on the part of the site to avoid any subject being lost to follow-up during the study. Before subjects are considered lost to follow-up, a minimum of 2 documented telephone contact attempts and 1 certified letter within 6 weeks of the most recent planned study visit must be sent in efforts to contact the subject. After being considered lost to follow-up, a subject's status may be changed if the subject makes contact at a later time provided the trial is ongoing.

7. STUDY ASSESSMENT AND PROCEDURES

7.1. Schedule of Events and Study Parameters

Table 2: Schedule of Events

Procedures	Screening ^a		Baseline	Placebo-controlled Phase					Long-term Extension Phase								Follow-up Phase ^b
	Day -42 to 0	Day -28	Day 0 up to +7 days	Week 2 ^c ±7 days	Week 4 & 8 ±7 days	Week 12 ±7 days	Week 16 & 20 ^c ±7 days	Week 24 ±7 days	Week 28 & 32 ^c ±7 days	Week 36 ±7 days	Week 40 & 44 ^c ±7 days	Week 48 ±7 days	Week 52 & 56 ^c ±7 days	Week 60 ±7 days	Week 64 & 68 ^c ±7 days	Week 72 ±7 days	Week 77 ±7 days
Informed consent	X							X									
Medical history	X																
Genetic confirmation of mitochondrial disease	X																
Inclusion/exclusion criteria	X																
12-lead ECG	X		X ^d					X ^d				X ^d				X ^d	
EEG	X ^e							X								X	
Height, weight, oxygen saturation	X ^f		X		X	X		X		X		X		X		X	
Physical exam and vital signs	X		X		X	X		X		X		X		X		X	
Pregnancy test ^g	X		X		X	X		X		X		X		X		X	X
Hematology (including CBC w/diffs)			X		X	X		X		X		X		X		X	
Coagulation panel	X		X		X	X		X		X		X		X		X	
Serum chemistry	X ^h		X		X	X		X		X		X		X		X	
Urinalysis	X		X		X	X		X		X		X		X		X	
Blood samples for PK analysis ⁱ			X					X				X				X	
Train caregiver on diary completion and hospitalization log	X ^j																
AE/SAE assessment ^k	X	X	X	X	X	X	X	X	X	X	X	X	X	X	X	X	X ^l
Concomitant medications	X		X	X	X	X	X	X	X	X	X	X	X	X	X	X	
Randomization			X														

Procedures	Screening ^a		Baseline	Placebo-controlled Phase					Long-term Extension Phase								Follow-up Phase ^b
	Day -42 to 0	Day -28	Day 0 up to +7 days	Week 2 ^c ±7 days	Week 4 & 8 ±7 days	Week 12 ±7 days	Week 16 & 20 ^c ±7 days	Week 24 ±7 days	Week 28 & 32 ^c ±7 days	Week 36 ±7 days	Week 40 & 44 ^c ±7 days	Week 48 ±7 days	Week 52 & 56 ^c ±7 days	Week 60 ±7 days	Week 64 & 68 ^c ±7 days	Week 72 ±7 days	Week 77 ±7 days
Seizure and dosing diary distribution	X																
Seizure and dosing diary collection/review		X	X	X	X	X	X	X	X	X	X	X	X	X	X	X	
Total hospital admissions and total hospital days for disease-related issues log	X	X	X	X	X	X	X	X	X	X	X	X	X	X	X	X	
CarerQoL-7D			X		X	X		X				X				X	
PedsQL			X					X								X	
Initiate dosing diary entry			X														
In-office dosing PO with food			X ^m					X ^m				X ^m				X ^m	
Dispense study drug			X ^m			X		X ⁿ		X		X		X			
Return of study drug bottles and drug reconciliation with dosing diary						X		X		X		X		X		X	

Abbreviations: AE, adverse event; ALT, alanine aminotransferase; AST, aspartate aminotransferase; CBC, complete blood count; COVID-19, coronavirus disease 2019; ECG, electrocardiogram; EEG, electroencephalogram; eCRF, electronic case report form; PedsQL, Pediatric Quality of Life Inventory™; PK, pharmacokinetics; SAE, serious adverse event; w/diffs, with differentials

^a Screening will be conducted and completed in a maximum of 42 days (up to 14 days Screening and 28 days Run-in period) prior to the Baseline Visit. Before the Run-in period subjects will be trained in diary completion. The Run-in phase and initiation of the seizure diary completed during this phase of the study, will contain a minimum of 28 consecutive days of seizure data collected prior to the Baseline Visit. Ideally the subject will be instructed to start entering diary information the day after Screening, so that the requisite number of days can be collected prior to the Baseline Visit. Laboratory tests from within 30 days of Screening are acceptable for entry to the study.

^b The follow-up visit will be conducted via telephone 30 days (±7 days) after last dose or termination visit.

^c Telephone call only.

^d ECG measurement will be performed at 4 hours postdose during each visit, time-matched to PK blood collection. Electrocardiogram should be performed approximately within 10 minutes preceding the 4-hour PK blood collection.

^e EEG for epilepsy confirmation if historical EEG up to 6 months prior to screening for confirmation of epilepsy is not provided.

^f Height will only be collected at the Screening Visit; all subsequent visits will collect weight and oxygen saturation only. Any change in weight of ≥10% from Baseline should result in dose adjustment. Weights ending in decimals ≥0.5 should be rounded up to the next whole number for dosing calculation.

^g Female subjects of childbearing potential must have a negative serum pregnancy test at Screening and a negative urine pregnancy test at all other indicated timepoints. If a subject cannot perform a urine pregnancy test at any timepoint, a serum pregnancy test should be performed. At-home urine pregnancy test kits will be provided; subjects will be required to perform the test at home 30 days after the last dose of study drug and self-report the results via telephone.

^h ALT, AST, and creatinine are the only chemistries required at the Screening Visit.

ⁱ Blood will be drawn for PK assessment predose and 1, 3, 4, and 8 hours postdose (prior to the next dose of vatiquinone) at Baseline and Week 24, and only 4 hours postdose at Weeks 48 and 72. For subjects weighing less than 10 kg, PK blood draw can be reduced to 2 timepoints per visit at the Baseline and Week 24 visits. Recommended timepoints are 0 (predose) hour and 4 hours postdose.

^j During the Screening Visit, the subject's caregiver will be trained on how to capture information in the seizure diary and hospital admissions log.

^k Serious adverse events will be assessed from the Screening Visit through 30 days following the last dose of study drug should be reported via the SAE report form to PTC within 24 hours of becoming aware of the event(s). In addition, the AE portion of the eCRF must also be completed.

^l The follow-up contact will be by telephone and should be completed 30 days (± 7 days) post last study drug administration or termination visit, whichever is later. Adverse events and SAEs will be followed until resolution or until they have normalized. At the investigator's discretion an office visit and additional tests may be conducted in order to ensure proper follow-up of an AE/SAE.

^m First dose for the placebo-controlled phase of the study will be taken the same day as the Baseline Visit. Study drug will be dispensed during the Baseline Visit and at each subsequent in-person visit. Drug may be delivered via delivery service if needed.

ⁿ From Week 24 onwards, vatiquinone will be dispensed to all subjects entering the long-term extension phase. Vatiquinone will be dispensed after completing the Week 24 assessments. The subjects will enter the open-label phase of the study and receive vatiquinone for the dose after the visit.

7.1.1. Screening Visit/Run-in Phase

Screening evaluations will be performed within a 42-day period (up to 14 days initial screening then 28 days Run-in) prior to the Baseline Visit. The investigator should inform each prospective subject of the nature of the study, explain the potential risks, and obtain written informed consent from the subject or parent(s)/legal guardian(s) prior to performing any study-related procedures and prior to the administration of study drug.

Screening (Day -42 to Day 0) evaluations will consist of the following:

1. Administer informed consent (Assent)
2. Assessment of eligibility
3. Chart review- previous medical history
4. Genetic confirmation of mitochondrial disease
5. Review inclusion and exclusion criteria
6. 12-lead ECG
7. EEG-diagnostic confirmation of epilepsy (historical EEG, up to 6 months prior to screening for, is acceptable)
8. Height, weight, and oxygen saturation
9. Physical Examination including vital signs
10. Serum pregnancy test: women of childbearing potential (WOCBP) must have a negative serum pregnancy test (see Section 7.4.3)
11. Laboratory assessments for coagulation, serum chemistry (ALT, AST, and creatinine only), and urinalysis (see Section 7.4.2)
12. The subject's caregiver will be trained on how to capture information in dosing diary, seizure diary, and hospital admissions log. The subjects will begin entering information in seizure diary daily and hospital admissions log during the Run-in phase. However, the subjects will begin entering information in dosing diary only after first dose.
13. SAE assessment
14. Concomitant medications assessment (last 30 days prior to screening)

During the first Screening Visit (occurring before Run-in), subjects will be instructed on how to complete the seizure diaries. To ensure the accuracy of diary entries during the study, subjects must complete at least 5 days of diary entries that will be reviewed prior to the Run-in period. Following diary review, at the discretion of the investigator and sponsor, a further diary entry training period can be implemented, until the investigator is satisfied that the seizures are correctly captured in the diaries, in which case the duration of Screening will be longer. Diary entries during this period are for training purposes and will not be included in the seizure count. The PTC medical monitor will closely review the seizure entry during the seizure training phase of the study and notify the principal investigators via e-mail to begin "Run-in" phase of the study for the subject. Seizures will be documented in an electronic seizure diary provided to each subject. Run-in will be a minimum of 28 days prior to the Baseline Visit.

7.1.2. Placebo-controlled Treatment Phase

If the subject has the required frequency of observable motor seizures during Run-in, meets all inclusion/exclusion criteria, and is willing to participate in the study, the subject will return for the baseline assessment and initiation of treatment with vatiquinone at a dose of 15 mg/kg if body weight <13 kg, and 200 mg if body weight \geq 13 kg, administered TID or placebo TID. In addition to the assessments listed below, all hospitalizations, total number of hospital days, total intensive care unit days and use of rescue antiepileptic medications will be tracked and recorded.

7.1.2.1. Baseline Visit/Randomization

The following assessments and procedures will be performed at Baseline Visit:

1. Review of all previous screening testing performed on the subject
2. 12-lead ECG at 4 hours postdose time-matched to pharmacokinetic (PK) blood collection; ECG should be performed approximately within 10 minutes preceding the 4-hour PK blood collection
3. Weight and oxygen saturation
4. Physical Examination including vital signs
5. Urine or serum pregnancy test: WOCBP must have a negative urine or serum pregnancy test (see Section 7.4.3)
6. Laboratory assessments for hematology, coagulation, serum chemistry, and urinalysis (see Section 7.4.2)
7. Randomization
8. The study drug will be administered at Baseline Visit by site staff or caregiver will be trained to administer the first dose on site
9. Blood samples drawn for PK analysis predose and 1, 3, 4, and 8 hours postdose (prior to the next dose of vatiquinone). For subjects weighing less than 10 kg, PK blood draw can be reduced to 2 timepoints per visit. Recommended timepoints are 0 (predose) hour and 4 hours postdose.
10. AE/SAE assessment
11. Concomitant medications assessment
12. Review of seizure diary
13. Calculation of total hospital admissions and total hospital days for disease-related issues from the time of the Screening Visit
14. CarerQoL-7D questionnaire
15. PedsQL questionnaire
16. Dispense study drug

During the Baseline Visit, study medication will be dispensed to the subject according to the randomization. First dose for the study drug will be taken the same day as Baseline Visit and PK samples collected during the Baseline Visit.

Subjects randomized to the treatment arm will be required to take study drug in a formulation mixed with sesame oil NF. Subjects in the placebo group will receive sesame oil with a colorant, which will have similar appearance and consistency as vatiquinone. In case the subject has a gastrostomy tube or nasogastric tube (G-tube or nasogastric tube) installed, vatiquinone or placebo will be administered using an amber oral dispenser into the G-tube with liquid food. If the subject is able to swallow, vatiquinone or placebo can be administered using an amber oral dispenser along with food.

7.1.2.2. Week 2 Visit (Day 14±1 week)

1. AE/SAE assessment
2. Concomitant medications assessment
3. Review of seizure and drug diaries
4. Calculation of total hospital admissions and total hospital days for disease-related issues

7.1.2.3. Week 4 Visit (Day 28 ± 1 week)

The following assessments and procedures will be performed at Week 4. A home health visit option may be performed at Week 4 if an in-person visit is not feasible due to travel or coronavirus disease 2019 (COVID-19) restrictions, etc.

1. Weight and oxygen saturation
2. Physical Examination including vital signs
3. Urine pregnancy test: WOCBP must have a negative urine pregnancy test (see Section 7.4.3). If a subject cannot perform a urine pregnancy test, a serum pregnancy test should be performed.
4. Laboratory assessments for hematology, coagulation, serum chemistry, and urinalysis (see Section 7.4.2)
5. AE/SAE assessment
6. Concomitant medications assessment
7. Review of seizure and dosing drug diaries
8. Calculation of total hospital admissions and total hospital days for disease-related issues
9. CarerQoL-7D questionnaire

7.1.2.4. Week 8 Visit (Day 56 ± 1 week)

The following assessments and procedures will be performed at Week 8. A home health visit option may be performed at Week 8 if an in-person visit is not feasible due to travel or COVID-19 restrictions, etc.

1. Weight and oxygen saturation
2. Physical Examination including vital signs

3. Urine pregnancy test: WOCBP must have a negative urine pregnancy test (see Section 7.4.3). If a subject cannot perform a urine pregnancy test, a serum pregnancy test should be performed.
4. Laboratory assessments for hematology, coagulation, serum chemistry, and urinalysis (see Section 7.4.2)
5. AE/SAE assessment
6. Concomitant medications assessment
7. Review of seizure and dosing drug diaries
8. Calculation of total hospital admissions and total hospital days for disease-related issues
9. CarerQoL-7D questionnaire

7.1.2.5. Week 12 Clinic Visit (Day 84 ± 1 week)

The following assessments and procedures will be performed at Week 12 (± 1 week):

1. Weight and oxygen saturation
2. Physical Examination including vital signs
3. Urine pregnancy test: WOCBP must have a negative urine pregnancy test (see Section 7.4.3). If a subject cannot perform a urine pregnancy test, a serum pregnancy test should be performed.
4. Laboratory assessments for hematology, coagulation, serum chemistry, and urinalysis (see Section 7.4.2)
5. AE/SAE assessment
6. Concomitant medications assessment
7. Review of seizure and dosing drug diaries
8. Calculation of total hospital admissions and total hospital days for disease-related issues
9. CarerQoL-7D questionnaire
10. Drug reconciliation of returned study drug bottles with dosing diaries
11. Dispense study drug

7.1.2.6. Week 16 Visit (Days 112 ± 1 week)

Week 16 assessments can be conducted by telephone and must include review of:

1. AE/SAE assessment
2. Concomitant medications assessment
3. Review of seizure and dosing drug diaries
4. Calculation of total hospital admissions and total hospital days for disease-related issues

7.1.2.7. Week 20 Visit (Days 140 ± 1 week)

Week 20 assessments can be conducted by telephone and must include review of:

1. AE/SAE assessment
2. Concomitant medications assessment
3. Review of seizure and dosing drug diaries
4. Calculation of total hospital admissions and total hospital days for disease-related issues

7.1.2.8. Week 24 Clinic Visit (Days 168 ± 1 week)

The following assessments and procedures will be performed at Week 24 (±1 week):

1. 12-lead ECG at 4 hours postdose time-matched to PK blood collection; ECG should be performed approximately within 10 minutes preceding the 4-hour PK blood collection
2. Weight and oxygen saturation
3. Physical Examination including vital signs
4. Urine pregnancy test: WOCBP must have a negative urine pregnancy test (see Section 7.4.3). If a subject cannot perform a urine pregnancy test, a serum pregnancy test should be performed.
5. Laboratory assessments for hematology, coagulation, serum chemistry, and urinalysis (See Section 7.4.2)
6. Blood samples drawn for PK analysis predose and 1, 3, 4, and 8 hours postdose (prior to the next dose of vatiquinone). For subjects weighing less than 10 kg, PK blood draw can be reduced to 2 timepoints per visit. Recommended timepoints are 0 (predose) hour and 4 hours
7. EEG
8. AE/SAE assessment
9. Concomitant medications assessment
10. Review of seizure and dosing drug diaries
11. Calculation of total hospital admissions and total hospital days for disease-related issues
12. CarerQoL-7D questionnaire
13. PedsQL questionnaire
14. Drug reconciliation of returned study drug bottles with dosing diaries
15. Informed consent if subject is continuing in Long-Term Extension phase
16. Dispense study drug if subject is continuing in Long-Term Extension phase

7.1.3. Long-Term Extension Phase (Study Weeks 36, 48, 60, and 72 are In-Person Visits and Study Weeks 28, 32, 40, 44, 52, 56, 64, and 68 are Telephone contact ± 1 week)

The subjects who are interested in continued treatment with vatiquinone will continue in the long-term extension phase of the study. In-person visits will occur every 12 weeks (± 1 week) and there will be every 4 weeks (± 1 week) telephone contact with the subject in between the in-person visits. Study medication will be dispensed at each in-person visit and will be sufficient to reach the next 12-week in-person visit.

The following assessments and procedures will be performed at each of the in-person visits under the long-term extension phase:

1. 12-lead ECG at 4 hours postdose time-matched to PK blood collection (Weeks 48 and 72 only; ECG should be performed approximately within 10 minutes preceding the 4-hour PK blood collection)
2. Weight and oxygen saturation
3. Physical examination including vital signs
4. Urine pregnancy test: WOCBP must have a negative urine pregnancy test (see Section 7.4.3). If a subject cannot perform a urine pregnancy test, a serum pregnancy test should be performed.
5. Laboratory assessments for hematology, coagulation, serum chemistry, and urinalysis (see Section 7.4.2)
6. Blood samples drawn for PK analysis 4 hours postdose at Study Weeks 48 and 72
7. EEG at Week 72
8. AE/SAE assessment
9. Concomitant medications assessment
10. Review of seizure and dosing drug diaries
11. Calculation of total hospital admissions and total hospital days for disease-related issues
12. CarerQoL-7D questionnaire will be collected at Study Week 48 and Study Week 72
13. PedsQL questionnaire (Week 72)
14. Drug reconciliation of returned study drug bottles with dosing diary (Study Weeks 36, 48, 60, and 72)
15. Dispense study drug (Weeks 36, 48, and 60)

The following assessments will be conducted at each of the telephone contacts and must include review of:

1. AE/SAE assessment
2. Concomitant medications assessment
3. Seizure and drug diaries

4. Calculation of total hospital admissions and total hospital days for disease-related issues

7.1.4. Post Treatment Follow-up Phase

The follow-up contact will be by telephone and should be completed 30 days (± 7 days) post last study drug administration or termination visit, whichever is later. Adverse events and SAEs whether or not deemed study drug-related will be followed until resolution or until they have normalized. At the investigator's discretion an office visit and additional tests may be conducted in order to ensure proper follow-up of an AE/SAE. Subjects will be closely monitored for possible rebound effects following discontinuation of study drug. Additionally, subjects who are WOCBP will be required to perform an at-home pregnancy test (study-provided) 30 days after the last dose of study drug and self-report the results via telephone.

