7.1.10. End of Treatment Visits

End of treatment visit takes place at Study Week 72 and includes the assessments listed in Section 7.1.2.1. Subjects who have an ongoing AE/SAE at the time of study completion will be followed for up to 30 days, until the event resolves, or until the sponsor and the Investigator agree that further follow-up is not medically necessary.

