7.5.8. Adverse Event Reporting

Investigator site reporting requirements for AEs are summarized in Table 6.

Table 6: Investigator Site Requirements for Reporting Adverse Events

Event	Recorded on the eCRF	Reported on the SAE/Pregnancy Report Form to PTC Pharmacovigilance Within 24 Hours of Awareness
Serious AE	All	All
Non-Serious AE	All	None
Exposure to the study drug during pregnancy or breastfeeding, and occupational exposure	All (regardless of whether associated with an AE), except occupational exposure	Exposure during pregnancy, exposure via breastfeeding, occupational exposure (regardless of whether associated with an AE)

Abbreviations: AE, adverse event; eCRF, electronic case report form; SAE, serious adverse event

All AEs should be followed up by the investigator until they are resolved, or the investigator assesses them as chronic or stable. The investigator should consider protocol guidelines and use his/her discretion in ordering additional tests as necessary to monitor the resolution of such events. In the event of additional investigations, the PTC Pharmacovigilance Department or designee should be informed via e-mail or fax. A subject withdrawn from the study because of an AE must be followed by the investigator until clinical recovery is complete and laboratory results have returned to normal, or until progression has been stabilized. Follow-up may need to continue after the subject has discontinued from the study, and additional investigations may be requested by the PTC medical monitoring team.

The first day of AE reporting will coincide with the date of signing of informed consent and including a minimum of 30 calendar days after the last administration of study drug.

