7.5.9. Serious Adverse Event Reporting

All SAEs occurring from the Screening Visit through 30 days following the last dose of study drug should be reported via the SAE report form to PTC within 24 hours of becoming aware of the event(s). In addition, the AE portion of the eCRF must also be completed.

The SAE report form should be signed by the investigator; however, if the investigator is unable to sign at the time of the event or within 24 hours, the form should be signed by the clinical staff member reporting the SAE (eg, the study coordinator). The SAE report form must be faxed or e-mailed to the PTC Pharmacovigilance Department or designee and to the site IRB/IEC (if required by local regulations) within 24 hours.

Follow-up information to the SAE should be clearly documented as “follow-up” in the SAE report form and must also be faxed or e-mailed to the same party. All follow-up SAE report forms for the event must be signed by the investigator. Any source documents (eg, progress notes, nurses’ notes, laboratory and diagnostic test results, discharge summaries) provided to the sponsor should be redacted so that the subject’s name, address, and other personal identity information are obscured. Only the subject’s study number and initials are to be provided (in regions where the provision of such information is permitted). The information in the AE portion of the eCRF and the SAE report form(s) must match or be reconciled. Where the same data are collected, the forms must be completed in a consistent manner. For example, the same AE term should be used on both forms.

In the rare event that the investigator does not become aware of the occurrence of an SAE immediately (for example, if a subject initially seeks treatment elsewhere), the investigator is to report the event within 24 hours after learning of it and to document his/her first awareness of the AE.

The PTC Pharmacovigilance Department contact information for reporting SAEs is provided below. This information is also provided in the Study Manual and in the SAE report form.

PTC Therapeutics Safety Department
Attention: Pharmacovigilance
E-mail: [contact]
[contact]

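### Close monitoring for rebound is promised after study drug stops, but the schedule provides one telephone AE check, which may fall up to 7 days before the 30-day reporting period ends

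*Protocol*

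**What the plan says.** Protocol 7.1.4 commits to rebound monitoring: "Subjects will be closely monitored for possible rebound effects following discontinuation of study drug". It gives no definition of rebound, no instrument and no frequency. The same section sets the contact: "by telephone and should be completed 30 days (± 7 days) post last study drug administration or termination visit, whichever is later". Section 3.1.5 and Table 2 footnote l repeat this. Footnote b leaves out the rule that the later date applies: "The follow-up visit will be conducted via telephone 30 days (±7 days) after last dose or termination visit". The column header in Table 2 reads Week 77 ± 7 days.

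In the follow-up column of Table 2, only the AE/SAE and pregnancy-test rows are marked. The row "Seizure and dosing diary collection/review", the concomitant-medication row and the hospital-log row are last marked at Week 72. The schedule in SAP Appendix 1 shows the same pattern.

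The reporting periods are longer than the earliest permitted call. For AEs, Protocol 7.5.8 specifies "including a minimum of 30 calendar days after the last administration of study drug"; for SAEs, 7.5.9 specifies "All SAEs occurring from the Screening Visit through 30 days following the last dose of study drug". SAP 6.2.1 also uses a 30-day limit for treatment-emergent events.

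Other protocol text points to wider collection than Table 2 shows. Section 7.1.8 has rescue medication collected for the whole study, inclusion criterion 3 asks for willingness to keep seizure diaries for the whole study, and 3.5 ends the study at the last follow-up visit.

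**The concern.** The sponsor names rebound as something to watch for, yet the schedule drops the instruments that would show it just when drug stops. In this population rebound would appear as more seizures, rescue use, status epilepticus or admissions. Each routine telephone contact in the extension (7.1.3) reviews AEs, concomitant medications, diaries, and hospital admissions and days. The one contact after treatment keeps only the first of these.

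Two things are at stake. First, without counts off drug that can be set against counts on drug, the trial could give only an impressionistic account of what happens on stopping. Second, a site that calls early in the window complies with the protocol but has not asked about the last days of the 30-day AE/SAE period, and no later contact is scheduled.

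**Working it through.** The plan gives no figure to reproduce. The check is a reading of Table 2 plus calendar arithmetic.

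**What is collected, by contact**

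| Item | Extension telephone contact (7.1.3) | Follow-up column, Table 2 |
|---|---|---|
| AE/SAE | yes | yes |
| Concomitant medication | yes | not marked |
| Seizure diary review | yes | not marked |
| Hospital admissions and days | yes | not marked |
| Pregnancy test (women of childbearing potential) | no | yes |

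The diary row has 15 marks, from Day -28 to Week 72, and then a blank. Week 72 also carries the in-office dosing mark, so a subject who completes on schedule has no diary review scheduled for any day after the last dose.

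**Contact window against reporting period**

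- Permitted call days after the anchor: 30 - 7 = 23 to 30 + 7 = 37, which is 15 calendar days.
- Reporting days left after the call = max(0, 30 - call day).
- Day 23: 30 - 23 = 7 days (7/30 = 23%). Day 27: 3 days (10%). Day 29: 1 day (3%). Day 30 or later: 0.
- Days 23-29 are 7 of the 15 permitted days (47%), with a mean shortfall of (1 + 2 + ... + 7)/7 = 4 days. Reading 47% as a share of calls would assume that calls spread evenly over the window, which the documents do not say.

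**Effect of the later-date rule.** If the termination visit is *k* days after the last dose, the earliest call is Day 23 + *k* after the last dose. The largest shortfall is max(0, 7 - *k*), which is zero once *k* reaches 7. The full 7 days therefore applies only when *k* = 0, as when the last dose is taken in the office at Week 72.

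**Table 2 header.** Week 72 is study day 72 × 7 = 504 and Week 77 is 77 × 7 = 539. The difference is 35 days, so ± 7 gives Days 28-42 after an on-time Week 72 visit, with a largest shortfall of 2 days. The text instead targets 504 + 30 = 534, or Week 76.3. Because Week 72 itself has a ± 7 day window, the header alone would permit 532 - 511 = 21 to 546 - 497 = 49 days after the actual visit.

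**Follow-up of ongoing events.** Sections 3.1.5 and 7.1.4 tie the end to resolution or normalisation. Sections 7.1.10 and 7.1.11 say such events "will be followed for up to 30 days, until the event resolves", and the sentence then adds a third alternative, agreement between sponsor and investigator. Section 6.2 has the same alternatives without the 30 days. Section 7.5.8 allows follow-up to stop when an event is judged chronic or stable.

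**The case against.** The strongest reply is that rebound would not go unseen, and that reply largely stands. A reader might infer from Table 2 that nothing about seizures is recorded after the last dose. The documents do not support that. Protocol 7.5.1 makes an increase in the frequency of a pre-existing condition's episodes a reportable AE, 7.5.4 has AEs asked about at any telephone contact, 7.5.9 requires SAEs to be sent within 24 hours of awareness, and 7.1.4 allows an office visit. The diary row also describes a site activity, so a missing mark does not prove that caregivers stop making entries. With the whole-study wording on rescue medication and diaries, this is an inconsistency to resolve rather than proof of absent data.

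Four further inferences should be resisted:

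- *Subjects who stop early have no off-drug seizure record.* The early termination visit uses the 7.1.2.1 assessments, which include diary review, medications and hospital days. Diary days between the last dose and that visit may exist.
- *An early call ends the site's duty.* A contact window is not a reporting period, and the 30-day duty continues after the call.
- *The Day 30 pregnancy result cannot be received.* It is self-reported by telephone, and nothing limits that report to the follow-up call.
- *Thirty days is a firm cap on AE follow-up.* The full sentence in 7.1.10 and 7.1.11 offers alternatives.

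It is also fair to say that rebound is neither an objective nor an endpoint, and that all subjects in the extension receive vatiquinone, so an off-drug comparison would have no control and could not separate rebound from progression.

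The objection does not remove the gap in measurement. AE capture would rest on recall over 23 to 37 days in response to an open-ended question, with no scheduled daily count. Section 7.5.2 also excludes admissions related only to disease progression from the hospitalisation criterion, so a seizure admission after stopping could escape SAE reporting when no hospital-log review is scheduled.

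**Conclusion.** The point holds as a mismatch between a stated safety commitment and the schedule. For Week 72 completers, no seizure counts, medication review or hospital data are scheduled off drug, and rebound would be captured only as recalled AEs. Early terminators are partly covered, up to their termination visit. Separately, the only scheduled contact may leave 1 to 7 of the 30 reporting days without active elicitation. The 7-day figure assumes that the last dose falls on the day of the final visit and that the site calls at the start of the window. The Week 77 header gives a different window again.

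The consequence is confined to safety information after treatment. The primary, key secondary and other Week 24 conclusions are untouched. The open-label SAP is a separate document not available here and may say more about analysis, but it could not supply data that the protocol does not schedule.

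**What to change.** 1. In Table 2 and 7.1.4, continue the existing electronic seizure diary and the hospital log to the follow-up contact, for completers and early terminators. Mark diary review, concomitant and rescue medication, and hospital-log review in the follow-up column. Summarise off-drug seizure frequency per 28 days descriptively against the last 28 days on drug, stating that there is no control group. The open-label SAP is the natural place for this.
2. Set the contact no earlier than Day 30 after the last dose, for example 30 to 37 days, in 3.1.5, 7.1.4 and Table 2 footnotes b and l. Align the Week 77 header and state the later-date rule the same way everywhere. A call on Day 30 or later leaves 0 of the 30 reporting days uncovered, against up to 7 now.
3. Reconcile the wording on follow-up of ongoing AEs in 3.1.5, 6.2, 7.1.4, 7.1.10, 7.1.11 and 7.5.8, so that a site can tell what role the 30 days play.

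The cost is protocol wording, about 30 more diary days for the caregiver, a longer call and some added diary review by site staff. No new visit or device is needed. Moving the call alone would close the AE gap but would not measure rebound, so items 1 and 2 belong together.
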